8.5 Treatment

8.5.1 Treatments Administered

The Investigator must ensure that the investigational products will be used only in accordance with the protocol.

Subjects will be randomly assigned at Baseline (day 1) to 1 of 3 treatment groups. The first dose will be administered as follows:

- Treatment A: ABP 798 1000 mg IV on study days 1 and 15
- Treatment B: Rituximab (US) 1000 mg IV on study days 1 and 15
- Treatment C: Rituximab (EU) 1000 mg IV on study days 1 and 15

At week 24, the subjects in treatment groups A and C will continue with and receive the second dose with the same treatment (ABP 798 1000 mg x 2 and rituximab (EU) 1000 mg x 2, respectively), and the subjects in treatment group B will transition to treatment group A1 and receive the second dose of ABP 798 1000 mg x 2. Retreatment may occur earlier, ie, anytime from week 16 to week 24 in individual subjects, if necessary in the opinion of the Investigator. The EOS will be at week 48 (or 24 weeks after the first infusion of the second dose for subjects retreated before week 24). A total of 2 doses will be administered during the study; each dose will consist of 2 infusions.

No dose reductions or changes will be allowed.

ABP 798/rituximab will be administered after all other procedures are completed for each visit. Investigational product will be administered only as an IV infusion by a healthcare professional with appropriate medical support to manage severe infusion reactions. Do

not administer as an IV push or bolus. Subjects should receive premedications before each infusion.

Premedications should be given according to local guidance and the approved product label. These should generally include acetaminophen and an antihistamine and methylprednisolone 100 mg IV or equivalent 30 minutes before each infusion.

IV infusions should be performed according to local guidance, and the approved product label (Rituxan Product Insert; MabThera Product Insert).

Investigational product infusion reactions should be handled according to local guidance and the approved product label.

All subjects will continue on a stable dose of MTX (\geq 7.5 mg/week, oral or subcutaneous [SC]) for the duration of their participation in the study, as prescribed by the treating physician. When possible, the dose of MTX should be taken on the same day of the week. In the event that a subject develops MTX-related side effects (eg, mucositis/stomatitis), a dose reduction or change of route should be considered.

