IgA, IgG, and IgM levels		X				X ⁱ	X ⁱ								X		X					X
Urinalysis	X	X						X									X					X
Tuberculosis testing	X																					
Pregnancy ^j	X	X						X								X	X			X	X	
Anti-CCP	X																					
Rheumatoid factor	X																					

Page 2 of 2

AE = adverse event; BL = Baseline; CRP = C-Reactive Protein; EOI = End of Infusion; EOS = End of Study; ESR = Erythrocyte sedimentation rate; h = hour; HAQ-DI = Health Assessment Questionnaire – Disability Index; HBsAg = Hepatitis B surface antigen; Anti-HBc = Hepatitis B core antibody; HCV = Hepatitis C virus antibody; Ig = Immunoglobulin, PK = Pharmacokinetic; Scn = Screening; VAS = Visual analogue scale; Anti-CCP= Anti-cyclic citrullinated peptide antibody

^a The second dose will be administered at week 24 or earlier, ie, anytime from week 16 to week 24, in individual subjects, if necessary in the opinion of the Investigator. For subjects who receive retreatment before week 24, all week 24 and post-week-24 assessments will be moved up to the corresponding time point after treatment (eg, week 26 will be 2 weeks after retreatment, week 30 will be 6 weeks after retreatment, etc.). An infusion may be delayed up to 7 days to allow for recovery from infection.

^b Subjects early terminating study should perform week 48 procedures.

^c Historical radiograph performed within 3 months prior to first dose of IP may be used and does not need to be repeated at screening ([section 10.7](#) for details)

^d ABP 798/rituximab dosing to be administered after all other procedures are completed for each visit.

^e Subjective assessments will be the first procedures performed at the visit.

^f Includes any other lab tests required only for screening. Creatinine clearance calculation will be performed only at screening.

^g Either CRP or ESR is required at screening. CRP will be performed by central lab and results will be blinded to study sites. ESR will be performed by local laboratory.

^h PK sampling: day 1, predose, at EOI, and 3 and 6 hours postdose; day 2 (24 hours postdose); day 3 (48 hours postdose); day 15, predose, at EOI, and 3, 6, and 24 hours postdose (day 16), and 48 hours postdose (day 17). In addition, at week 4 (day 29), week 8 (day 57), week 12 (day 85), and predose week 24, week 26, and week 30, 48/EOS. Blood sampling for PK analysis during each return visit, including the EOS visit, will occur per the scheduled time point with tolerance collection

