## 3. STUDY DESIGN

This is a randomized, double-blind, active-controlled 3-arm study in adult subjects with moderate to severe Rheumatoid Arthritis (RA) who have an inadequate response or intolerance to other disease-modifying anti-rheumatic drugs (DMARDs), which must include intolerance or inadequate response to one or more tumor necrosis factor (TNF) inhibitor therapies.

Sponsor: Amgen Inc.

Statistical Analysis Plan

Protocol No: 20130108

10-December-2018/ Version 2.0

---

Approximately 300 subjects (100 per treatment group) will be enrolled. The subjects will be randomized to receive either 2 IV infusions of ABP 798, 1000 mg each, given 2 weeks apart (treatment group A), or 2 IV infusions of rituximab (US) 1000 mg each, given 2 weeks apart (treatment group B) or 2 IV infusions of rituximab (EU), 1000 mg each, given 2 weeks apart (treatment group C) in a double blind fashion. A total of 2 doses will be administered during the study; each dose consists of 2 infusions, 2 weeks apart.

An independent data monitoring committee (DMC) will evaluate the safety data throughout the study, including an initial safety analysis after the first 18 subjects have received the first dose (1000 mg x 2 infusions of either ABP 798 or rituximab (EU) or rituximab (US)).

At week 24, the subjects in treatment groups A and C will continue with and receive the second dose of the same treatment, and the subjects in treatment group B will transition to treatment group A1 and receive ABP 798 1000 mg x 2 as their second dose.

Retreatment may occur earlier, i.e., anytime from week 16 to week 24, in individual subjects, if necessary in the opinion of the Investigator.

The end of study (EOS) will be at week 48 (or 24 weeks after the first infusion of second dose for subjects retreated before week 24), and a final analysis will be performed when all subjects have completed or have had the opportunity to complete the week 48/EOS assessments.

See [Figure 1](#) below for a summary of the study design.

[figure not shown]

Sponsor: Amgen Inc.

Statistical Analysis Plan

Protocol No: 20130108

10-December-2018/ Version 2.0

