## 5.2 PHARMACOKINETIC

Pharmacokinetic parameters will be calculated from serum concentration-time data using noncompartmental analysis (NCA) methods using Phoenix WinNonLin® Version 6.4 or higher (Pharsight Corp, St. Louis, MO). The following PK parameters will be reported for serum rituximab and ABP 798, using actual elapsed sampling times:

Variable	Definition
$C_{max1}$	Maximum observed serum concentration following Dose 1 Infusion 1
$C_{max2}$	Maximum observed serum concentration following Dose 1 Infusion 2
$t_{max1}$	Time to which the maximum serum concentration was observed following Dose 1 Infusion 1
$t_{max2}$	Time to which the maximum serum concentration was observed following Dose 1 Infusion 2
TLST1	Time of last quantifiable concentration following Dose 1 Infusion 1

Sponsor: Amgen Inc.

Protocol No: 20130108

Statistical Analysis Plan

10-December-2018/ Version 2.0

CLST1	Last quantifiable concentration following Dose 1 Infusion 1 over first 14 days postdose (day 15)
AUC 0-14 day	Area under the serum concentration-time curve from time 0 on day 1 prior to the first infusion of the first dose to last quantifiable concentration associated with Dose 1 Infusion 1 over the first 14 days postdose (day 15)
TLST2	Time of last quantifiable concentration associated with Dose 1 Infusion 2
CLST2	Last quantifiable concentration after Dose 1 Infusion 2
AUC 0-12 wk	Area under the serum concentration-time curve from time 0 on day 1 prior to the first infusion of the first dose to last quantifiable concentration over 12-week profile
AUC inf	Area under the serum concentration-time curve from time 0 on day 1 prior to the first infusion of the first dose extrapolated to infinity; calculated as AUC last + CLST2/λ z , where AUC last is the AUC from time 0 to the last quantifiable concentration up to week 12 (i.e. AUC 0-12 wk )
t 1/2	Terminal elimination half-life determined from time 0 to Week 12 profile; calculated as ln(2)/ λ z
λ z	Terminal elimination rate constant
CL	Clearance
AUMC	Area under the first moment curve
MRT	Mean residence time; calculated as AUMC inf /AUC inf – TI /2, where TI represents infusion duration and AUMC inf is the area under the moment curve from the time of first dosing extrapolated to infinity.
AUC 0-12 wk /AUC inf	calculated as AUC 0-12 wk /AUC inf

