AUC% extrap	Percent of AUC extrapolated to infinity in AUC inf

Following administration, Cmax, tmax, CLST and TLST will be obtained directly from the experimental observations. If multiple maxima occur at equal concentrations after an infusion, the first temporal value will be used.

AUC0-14 day, AUC0-12 wk and AUCinf will be estimated using the linear trapezoidal rule.

Values of AUC0-14 day and Cmax associated with Dose 1 Infusion 2 will be listed but excluded from descriptive statistics and statistical analysis if the time of the last concentration following Dose 1 Infusion 1 is outside ± 2 day window around Day 15.

Sponsor: Amgen Inc.

Statistical Analysis Plan

Protocol No: 20130108

10-December-2018/ Version 2.0

Values of  $AUC_{0-12\text{ wk}}$  will be listed but excluded from descriptive statistics and statistical analysis if the time of the last concentration following Dose 1 Infusion 2 is outside  $\pm 2$  week window around Week 12.

The terminal half-life,  $t_{1/2}$ , where determined, will be calculated as  $\ln(2)/\lambda_z$ . The number of data points included in the regression will be determined by visual inspection, but a minimum of three data points in the terminal phase, excluding  $C_{\max}$ , will be required to estimate  $\lambda_z$ .  $\lambda_z$  values (and consequently  $t_{1/2}$  and  $AUC_{\text{inf}}$  values) will be considered unreliable estimates if the time period over which an individual  $\lambda_z$  was required is less than twice the resultant  $t_{1/2}$  or the adjusted coefficient of determination 'Rsq' is less than or equal to 0.8. Additional exclusions of PK parameters, if any, will be described in the CSR.

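### The SAP's mean residence time formula corrects for one infusion although the profile covers two, so it omits half the inter-infusion interval (7 days at the planned spacing)

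*SAP*

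**What the plan says.** The parameter table in SAP 5.2 gives MRT as AUMCinf/AUCinf minus TI/2, "where TI represents infusion duration". The same entry says that AUMCinf "is the area under the moment curve from the time of first dosing extrapolated to infinity". AUCinf is the "Area under the serum concentration-time curve from time 0 on day 1 prior to the first infusion of the first dose extrapolated to infinity", and its extrapolated part uses CLST2, the "Last quantifiable concentration after Dose 1 Infusion 2". Both areas therefore span both infusions of the first dose.

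SAP 3 describes the regimen as "2 IV infusions of ABP 798, 1000 mg each, given 2 weeks apart"; the two rituximab arms have the same pattern. Protocol 8.5.1 sets the days: "ABP 798 1000 mg IV on study days 1 and 15", and likewise for the other arms. A footnote to the schedule in Protocol 8.6.1.1 adds that "An infusion may be delayed up to 7 days to allow for recovery from infection".

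SAP 4.2.1 lists MRT among the additional PK endpoints. SAP 9.5.2 summarizes it by treatment, including a geometric mean and geometric CV. Protocol 8.6.1.1 and 12.6.4 do not list it.

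**The concern.** Measured from the first infusion, AUMCinf/AUCinf is not residence time alone. It is residence time plus the mean time at which the drug entered the body. For one infusion that mean input time is TI/2, which is what the SAP subtracts. Here, half of the drug enters 14 days later, and nothing in either document removes that delay.

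At stake are the MRT values in the study report. They would be shifted upward in all three arms, and the added constant would also shrink relative quantities, namely the geometric CV and any between-arm ratio.

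**Working it through.** The documents state no MRT value, so there is no figure to reproduce. The check is on the formula.

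**Inputs from the documents.** Two equal 1000 mg infusions; interval tau = 14 days; a permitted delay of up to 7 days; AUCs that "will be estimated using the linear trapezoidal rule" (SAP 5.2); PK samples through week 12 as in Protocol Table 1.

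**Assumptions, because the documents do not give them.** Half-life 10 to 25 days; infusion duration 3 to 6 hours; linear trapezoids for AUMC as well; terminal slope from weeks 4, 8 and 12. The bi-exponential cases give half the amplitude to a fast phase with a half-life of 1.5 days.

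**Step 1: exact moments.** Let A and M be the AUC and AUMC of one dose given as a bolus, so that true MRT = M/A. With linear kinetics and two equal infusions of duration TI starting at 0 and tau:

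- AUC = 2A
- AUMC = (M + A·TI/2) + (M + A·(tau + TI/2))
- AUMC/AUC = M/A + TI/2 + tau/2

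Subtracting TI/2 leaves M/A + tau/2. At tau = 14 days the excess is 14/2 = 7.0 days, whatever the half-life or TI. For comparison, TI/2 removes only 1.5 to 3 hours.

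**Step 2: other intervals.** The excess is tau/2: 6 days at 12, 8 days at 16, and 10.5 days at 14 + 7 = 21. If kinetics are not linear, it is about 14 days times the second infusion's share of total AUC: 7.7 days at a 55% share, 8.4 days at 60%.

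**Step 3: the protocol's sampling times.** Apply the same formula to concentrations at the scheduled times, with linear trapezoids and the extrapolated tail. Values are in days, for TI = 3 h; differences were taken before rounding.

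| Half-life, disposition | True MRT | SAP formula, exact moments | SAP formula, sampled | Net excess, sampled |
|---|---|---|---|---|
| 10, mono | 14.43 | 21.43 (+49%) | 19.90 | 5.48 |
| 15, mono | 21.64 | 28.64 (+32%) | 26.79 | 5.15 |
| 20, mono | 28.85 | 35.85 (+24%) | 33.99 | 5.13 |
| 25, mono | 36.07 | 43.07 (+19%) | 41.33 | 5.26 |
| 10, bi | 12.83 | 19.83 (+55%) | 17.82 | 4.99 |
| 15, bi | 19.87 | 26.87 (+35%) | 24.30 | 4.43 |
| 20, bi | 26.99 | 33.99 (+26%) | 31.23 | 4.24 |
| 25, bi | 34.15 | 41.15 (+20%) | 38.38 | 4.24 |

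Across infusions of 3 to 6 hours the net excess is about 4.2 to 5.5 days. The interpolation error is the net excess minus 7, that is, about -1.5 to -2.8 days.

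**Step 4: effect of an added constant.** Take a true MRT of 28.85 days and the 7-day formula term. A 30% CV is an SD of 8.66 days, which becomes 8.66/35.85 = 24%. A true between-arm ratio of 0.80 becomes (0.80 × 28.85 + 7)/35.85 = 0.84.

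**The case against.** **The 7 days is not what would be reported.** A reader might infer that every reported MRT will be 7 days too long. The documents do not support that: with the planned sampling and linear interpolation, the assumed cases give 4.2 to 5.5 days. At a one-compartment half-life of 20 days the excess is 5.13/28.85 = 18%, not 24%. This stands. But the two errors have separate causes, and a partial accidental offset does not justify the formula.

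**The shift is not one constant.** This also stands. It follows each subject's actual interval and the dose actually given. The PK parameter set in SAP 6.5 requires only the full Day 1 dose, and SAP 9.5.2 allows that some parameters may not be reportable after an incomplete infusion. Where the profile contains only infusion 1, TI/2 is right.

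**MRT will contradict the reported clearance or half-life.** This is tempting but unsupported. MRT links to clearance only through a steady-state volume, which is not on the SAP's list. MRT equals half-life/ln 2 only for one compartment; in the bi-exponential cases above, the true MRT is already 5 to 11% below that value.

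**Nothing planned depends on MRT.** Largely true. SAP 9.5.2 plans ratios and 90% CIs for AUCinf, Cmax, AUC0-14 day and AUC0-12 wk. Read literally, its per-protocol sensitivity analysis covers all PK parameters and so would include MRT, but no decision rests on that.

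**TI could mean the whole input period.** Only that reading would repair the formula, and the SAP's words do not say it. Adding the two infusion durations together would still remove only hours.

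**Conclusion.** The point holds as an error in a stated formula. Under linear kinetics with two equal full infusions, the SAP's MRT omits tau/2, which is 7.0 days at the planned spacing and 10.5 days after a 7-day delay. The expected net excess in reported values is smaller, about 4.2 to 5.5 days, and that range depends on the assumed half-lives, infusion durations, disposition shapes and AUMC rule.

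The consequence is minor. The formula is the same in all arms, and MRT is descriptive in the main analysis. A reader might infer a threat to biosimilarity; there is none, because AUCinf and Cmax do not use this formula. What is distorted is the MRT summary itself: its level, its geometric CV and any ratio read from it.

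**What to change.** In SAP 5.2, replace TI/2 with the dose-weighted mean input time:

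MRT = AUMCinf/AUCinf - MIT, with MIT = sum[Di·(si + TIi/2)] / sum[Di].

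Here si is the actual start of infusion i measured from first dosing, TIi its duration and Di the dose given, summed over the infusions in the profile. For two equal full infusions 14 days apart, MIT = TI/2 + 7 days. If only infusion 1 is in the profile, it reduces to TI/2. Dose weighting matters: if, say, half of the second infusion were given, the interval term would be 14 × 500/1500 = 4.7 days rather than 7.

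The SAP should also state the integration rule for AUMC. The corrected formula does not remove the interpolation error, so in the assumed cases MRT would still come out about 1.5 to 2.8 days short.

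Otherwise, drop MRT from the parameter list, or label it as not corrected for the two-infusion input.

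The cost is one line of SAP text and minor programming. No new data are needed: the SAP already works from actual sampling times, infusion stop times and doses received.

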10.9 Blood Samples for Pharmacokinetic Analysis

During treatment, a series of serum samples will be taken according to [Table 1](#). The exact times of blood sampling will be recorded.

Blood sampling for PK analysis during each return visit, including the EOS visit, will occur per the scheduled time point with tolerance collection windows as follows:

- predose day 1 = within 1 hour prior to dosing
- days 1 and 15 at EOI - infusion should be monitored to ensure collection of the PK sample within 10 minutes after the end of the infusion
- all other day 1 sampling times = \pm 10 minutes
- days 2 and 3 = \pm 3 hours
- predose day 15 = within 1 hour prior to dosing
- all other day 15 sampling time = \pm 10 minutes
- days 16 and 17 = \pm 3 hours
- weeks 4, 8, and 12 = \pm 2 days
- predose at weeks 24 and 26 = within 1 hour prior to dosing
- weeks 30 and 48 = \pm 2 days

Details of the procedures to be followed for sample collection, storage, and shipment will be documented in the Laboratory Manual.

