### 9.5.2 Pharmacokinetic Parameters

PK parameters for ABP 798 and rituximab will be estimated using noncompartmental analysis methods with Phoenix WinNonlin® Version 6.4 or higher (Pharsight Corp., St. Louis, MO).

In the event that a subject does not receive the full protocol-specified infusion, subsequent PK samples may be considered not evaluable and thus certain PK parameters may not be reportable. In addition, if the full protocol-specified dose was given but there was a long dose interruption or unusually long infusion duration that was deemed to impact PK, the PK profile may be considered not evaluable. The subject exclusion from the PK parameter analysis set will be determined based on a blinded data review prior to unblinding for the final analysis. Any such exclusion will be clearly listed in the CSR along with justification for exclusion.

Pharmacokinetic parameters will be listed by subject and summarized descriptively by treatment for the PK parameter analysis set. The following descriptive statistics will be provided: n, arithmetic mean, SD, Q1, Q3, minimum, median and maximum. Only n, median, Q1, Q3, minimum and maximum will be reported for  $t_{max}$ . In addition, geometric mean, and geometric CV will be calculated for  $AUC_{inf}$ ,  $AUC_{0-14\ day}$ ,  $AUC_{0-12\ wk}$ ,  $C_{max}$ ,  $CLST2$ ,  $t_{1/2}$ ,  $\lambda z$ , CL, MRT,  $AUC\%extrap$  and  $AUC_{last}/AUC_{inf}$ .

The serum PK parameters will be estimated from the individual concentration data for all subjects in the PK parameter analysis set. In estimating the PK parameters, BQL values at

Sponsor: Amgen Inc.

Statistical Analysis Plan

Protocol No: 20130108

10-December-2018/ Version 2.0

the beginning of the profile will be set to zero. BQL values that occur after the first quantifiable point will be considered missing. Actual sampling times will be used in all computations.

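### The linear trapezoidal rule across 12- and 28-day sampling gaps pulls the primary AUCinf ratio towards 1 if the products differ in clearance

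*SAP*

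**What the plan says.** SAP section 5.2 derives the PK parameters by noncompartmental methods from actual sampling times. It states that AUC0-14 day, AUC0-12 wk and AUCinf "will be estimated using the linear trapezoidal rule". AUCinf is AUClast plus CLST2/λz, where AUClast "is the AUC from time 0 to the last quantifiable concentration up to week 12". The terminal slope needs "a minimum of three data points in the terminal phase, excluding" Cmax.

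The footnotes to the schedule of assessments (Protocol section 8.6.1.1) place samples at end of infusion and 3, 6, 24 and 48 hours after each of the two infusions, which are given on days 1 and 15. The later samples are then listed: "In addition, at week 4 (day 29), week 8 (day 57), week 12 (day 85), and predose week 24". Inside AUCinf this leaves gaps of about 12 days (day 3 to 15 and day 17 to 29) and two gaps of 28 days (day 29 to 57 and day 57 to 85).

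AUCinf is a primary endpoint. Similarity requires the 90% CI of the geometric mean ratio to lie within 0.80 to 1.25, at 0.05 for each of the US and EU comparisons (Protocol sections 12.2 and 12.6.4). The PK sensitivity analyses in SAP section 9.5.2 change the analysis set, the covariates or the ADA subgroup. None changes the integration rule.

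**The concern.** The plan treats the terminal phase as log-linear when it extrapolates with CLST2/λz and computes half-life as ln(2)/λz, but it integrates the same declining limb with straight lines. Over a 28-day gap that adds area, and it adds proportionally more for a subject who clears faster. When two products differ in clearance, the overstatement therefore does not divide out of the ratio. The lower-exposure arm is raised more, and the ratio reads closer to 1 than it is. In a similarity test that is the anti-conservative direction, on a primary endpoint.

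The same AUCinf also enters the US-to-EU comparison, which decides whether the reference arms are pooled for the efficacy analysis (SAP section 9.7). Cmax after the second infusion offers little protection: with 25% faster clearance its ratio is still about 0.94 to 0.97.

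**Working it through.** **Inputs from the documents.** Sampling times and AUCinf formula as above; CV 40%; margin 0.80 to 1.25; 0.05 per comparison; 300 subjects randomized 1:1:1 with 15% dropout, so 100 × 0.85 = 85 per arm.

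**Assumptions.** The half-life is not in the documents; 14 to 25 days is taken. Infusion time is set at 4 hours. AUCinf values that section 5.2 would call unreliable are kept.

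**The plan's own figure.** The log-scale SD is √ln(1 + 0.4²) = 0.385. Two one-sided t-tests at a true ratio of 1 give power of 96.6% at 85 per arm (98.5% at 100) per comparison and endpoint. The stated power above 90% is reproduced.

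**Error over one gap.** For an exponential fall at rate k over a gap Δ, with x = kΔ:

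linear area / exact area = (x/2) · coth(x/2)

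At a half-life of 18 days, k = 0.6931/18 = 0.0385 per day.
- 28-day gap: x = 1.078, factor 1.095.
- 28-day gap with clearance 25% faster: x = 1.348, factor 1.147.
- 12-day gap: x = 0.462, factor 1.018.

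**Error in AUCinf.** The full two-infusion, one-compartment profile was sampled at the protocol times, integrated linearly, and extended by CLST2/λz. The result was compared with the true value, which is proportional to 2 × dose/clearance. At 18 days AUCinf is overstated by 4.6%, of which 3.9 points come from the 28-day gaps.

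**Effect on the ratio and the test.** Let the test product clear 25% faster, so that the true ratio is 1/1.25 = 0.80. Then:

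ratio read = 0.80 × (overstatement, faster arm) / (overstatement, reference arm)

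SE = 0.385 × √(2/85) = 0.0591

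P(pass) ≈ Φ(−1.645 + ln(ratio read/0.80)/SE)

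At 18 days the ratio read is 0.80 × 1.0662/1.0465 = 0.815. The shift is ln(0.8151/0.80) = 0.0187, and 0.0187/0.0591 = 0.316. Φ(−1.329) = 9.2%.

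| Half-life (days) | Overstated, reference | Overstated, faster arm | True 0.80 reads as | P(pass), nominal 5% |
|---|---|---|---|---|
| 14 | 6.9% | 9.4% | 0.819 | 10.4% |
| 18 | 4.6% | 6.6% | 0.815 | 9.2% |
| 22 | 3.3% | 4.8% | 0.812 | 8.2% |
| 25 | 2.6% | 3.9% | 0.810 | 7.7% |

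With linear-up/log-down the one-compartment ratio reads 0.800 and P(pass) is 5% in every row.

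**Two compartments.** The distribution parameters also have to be assumed. Illustrations give P(pass) of about 9 to 18% with the linear rule and about 6 to 8% with log-down.

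**Both comparisons.** If the true ratio is 0.80 against each of two identical references, the simulated chance of passing both rises from about 1% to 2 to 4% (one compartment).

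**Where the bias cancels.** If the products differ only in delivered content, the curves have the same shape and a true 0.80 reads as 0.80. With equal clearance and a true ratio of 1, the ratio reads 1.

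**The case against.** The linear rule is a defined, prespecified noncompartmental option, and under the planning assumption of a true ratio of 1 it introduces no pull. That stands. A reader might infer that the AUCinf ratio is always biased towards 1; the effect needs a clearance difference.

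The shift in the ratio is small: 0.01 to 0.02 with one compartment and up to about 0.03 with two. That also stands. It matters only near the limits.

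The primary objective names both references, so passing one comparison is not enough. A reader might infer that the trial's overall false-positive rate exceeds 5%. The calculation does not support that when US and EU rituximab are alike, because the joint rate stays at 2 to 4%. But the documents set 0.05 for each comparison, and that level is exceeded. The joint figure gives no assurance if the references differ.

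A clearance difference would not be hidden altogether. λz and half-life come from the terminal regression, which the trapezoidal rule does not touch, and both are summarised by treatment. They are descriptive, however, and do not enter the decision.

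The restoration to 5% depends on keeping flagged values. Section 5.2 calls λz, and with it AUCinf, unreliable when the fitted period is under twice the half-life. A fit over days 29 to 85 spans 56 days, so half-lives above 28 days are flagged, and these are mostly slow clearers. The SAP does not say explicitly whether such values are dropped. If they are, a one-compartment simulation (three terminal points, 10% assay error assumed) gives per-comparison pass rates at a true 0.80 of 11%, 25% and 47% with log-down, at half-lives of 14, 18 and 22 days. The linear rule gives 23%, 41% and 62%. The linear rule still adds to the error, but log-down alone would not hold 5%.

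**Conclusion.** The point holds in conditional form. The rule and the schedule are both explicit in the documents. Together they move the AUCinf ratio towards 1 whenever the products differ in clearance, and no planned analysis would show it. With an assumed half-life of 14 to 25 days, one compartment, 85 per arm, 40% CV and flagged values kept, a true 0.80 reads as 0.81 to 0.82. The per-comparison pass probability at the limit is then about 8 to 10% instead of 5%. The two-compartment range of 9 to 18% is illustrative only.

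This is a modest weakness in a primary derivation, worth correcting because it acts in one direction and is cheap to remove. It does not show that a similarity conclusion would be wrong. Nor does it show that log-down removes the whole error: with two compartments about 6 to 8% remains.

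**What to change.** Before unblinding, amend SAP section 5.2 to specify the linear-up/log-down trapezoidal rule for AUC0-14 day, AUC0-12 wk, AUCinf and AUMC, and keep the linear rule as a sensitivity analysis. At a minimum, prespecify log-down AUCinf as a sensitivity analysis in section 9.5.2, for all three pairwise comparisons.

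The cost is one SAP sentence and one setting in the noncompartmental software, with no new data. The downside is that the values become less directly comparable with studies that used the linear rule; reporting both versions meets that.

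### A missing day-15 predose sample inflates AUC0-12wk and the co-primary AUCinf under the written linear trapezoidal rule, and the SAP's Day 15 exclusion does not extend to either

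*SAP*

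**What the plan says.** SAP 5.2 defines AUCinf as "Area under the serum concentration-time curve from time 0 on day 1 prior to the first infusion of the first dose extrapolated to infinity". It is the sum of a measured part and CLST2/λz, where the measured part "is the AUC from time 0 to the last quantifiable concentration up to week 12". One integral therefore spans infusion 1, infusion 2 and the decline to week 12. The same section states that all three AUCs "will be estimated using the linear trapezoidal rule".

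Protocol Table 1 (footnote h, Section 8.6.1.1) places no PK sample between the 48-hour draw on day 3 and the predose draw on day 15. The next sample after that is at the end of infusion 2.

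SAP 5.2 has two window rules and one reliability rule:
- AUC0-14day and infusion-2 Cmax are listed but not analysed "if the time of the last concentration following Dose 1 Infusion 1 is outside" a ±2-day window around Day 15.
- AUC0-12wk is listed but not analysed "if the time of the last concentration following Dose 1 Infusion 2 is outside" a ±2-week window around Week 12.
- λz, and with it AUCinf, is unreliable if the fitted span is less than twice the half-life or the adjusted Rsq is 0.8 or lower.

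**The concern.** When the day-15 predose sample was not drawn or was lost, the last concentration after infusion 1 is the 48-hour value. The next point in the profile is the infusion-2 peak. The trapezoid between them rises while the true concentration falls, so the error is always upward.

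The Day 15 rule responds to exactly this situation, but with an odd result. It removes infusion-2 Cmax, which is observed directly and does not depend on the trough. It keeps AUCinf, which the lost sample distorts. Both are co-primary. AUCinf also feeds the US-EU similarity decision, which determines whether the two reference arms are pooled for the DAS28-CRP comparison (SAP 9.7).

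**Working it through.** **1. The plan's own PK figure.** Inputs from Protocol 12.2: CV 40%, true GMR 1, margin 0.8 to 1.25, 15% dropout, α 0.05 per comparison.
- Log-scale SD = √ln(1 + 0.40²) = 0.385.
- n per arm = 100 × 0.85 = 85.
- SE = 0.385 × √(2/85) = 0.0591.
- Power ≈ 2Φ(0.2231/0.0591 − 1.645) − 1 = 96.7%, or 96.5% using the t distribution.

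This agrees with the stated power above 90%, which is not in dispute.

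**2. Which rule responds to a missing day-15 predose sample?**

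| Parameter | Criterion in SAP 5.2 | Triggered? |
|---|---|---|
| AUC0-14day | last infusion-1 sample within Day 15 ± 2 days | yes, excluded |
| Infusion-2 Cmax | same | yes, excluded |
| AUC0-12wk | last infusion-2 sample within Week 12 ± 2 weeks | no |
| AUCinf | λz span and Rsq | no; λz is fitted to the late samples and does not use the predose value |

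**3. Size of the error in one subject.** Let Δ1 be the time from the 48-hour sample to predose and Δ2 the infusion-2 duration. Subtracting the two trapezoid sums gives

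excess = ½Δ1(C_EOI2 − C_pre) + ½Δ2(C_48h − C_pre).

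Assumed infusion durations are 4.25 h and 3.25 h, so Δ1 = 14 − 0.18 − 2 = 11.82 days and Δ2 = 0.135 day. Concentrations are in units of dose over central volume.

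- *One compartment, half-life 18 d.* C_48h 0.923, C_pre 0.585, C_EOI2 1.580. Excess = ½ × 11.82 × 0.994 + ½ × 0.135 × 0.337 = 5.90. AUCinf by the same rule with the sample present is 54.35. Overstatement = 5.90/54.35 = 10.9%.
- *Two compartments, terminal half-life 18 d, half the initial concentration in a fast phase of half-life 2 d.* C_48h 0.704, C_pre 0.297, C_EOI2 1.282. Excess = ½ × 11.82 × 0.985 + ½ × 0.135 × 0.407 = 5.85. AUCinf with the sample is 31.66. Overstatement = 18.5%.

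Over the assumed ranges (fast phase 0 to 60% of the initial concentration, with half-life 0.5 to 3 d):

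| Shape and terminal half-life | Against the same rule with the sample | Against the exact AUC |
|---|---|---|
| One compartment, 14–22 d | 9% to 14% | 13% to 22% |
| Two compartments, 14–22 d | 11% to 30% (median 17%) | 15% to 46% (median 25%) |
| Both shapes, 10–28 d | 7% to 40% | 9% to 63% |

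The last column also contains the linear rule's ordinary bias on a declining curve (about 2% to 11% for one compartment, 10–28 d), which is a separate matter.

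**4. Effect on an arm's geometric mean.** With k of 85 subjects overstated by a fraction e, the factor is exp[(k/85) ln(1 + e)].
- k = 1: 1.0018 at e = 17% and 1.0034 at e = 34%.
- k = 5: 1.0093 at e = 17% and 1.0174 at e = 34%. At the ends of the range, exp(0.0588 × ln 1.07) = 1.004 and exp(0.0588 × ln 1.40) = 1.020.

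Equal rates in both arms largely cancel in the GMR and leave only a small increase in variance.

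**5. The two remedies.**
- *Exclusion.* With 5 subjects lost per arm, n = 80 and SE = 0.385 × √(2/80) = 0.0609. Power is 95.6% by the normal approximation and 95.4% with the t distribution.
- *Inserted trough*, C_48h × exp(−λz × Δ1). In the two-compartment example this is 0.704 × exp(−0.0387 × 11.82) = 0.445 against a true 0.297. Residual error = ½ × 11.96 × 0.148/31.66 = 2.8%, compared with 18.5% uncorrected. Over the ranges above it stayed at about 4% or less, and at zero for one compartment.

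**The case against.** The plan does have routes by which such a value could be removed. The PK parameter set requires an evaluable profile, with exclusions settled at blinded review before lock (SAP 6.5). A per-protocol PK set drops subjects with important deviations affecting PK and is re-analysed as a sensitivity analysis (SAP 6.6 and 9.5.2). SAP 5.2 also allows additional parameter exclusions, to be described in the CSR. This stands as far as it goes, and it would be wrong to say that nothing in the plan could catch the problem. But evaluable is not defined, the examples in SAP 9.5.2 concern incomplete, interrupted or prolonged infusions, and the CSR exclusions have no criterion or timing. None of them says what to do about a missing trough.

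Missed samples should also be uncommon. The predose draw is a listed procedure within 1 hour of dosing, and the infusion follows all other procedures (Protocol 8.5.1, 9.5 and 10.9). That stands too.

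Three stronger readings are tempting but not supported:
- *That the same range covers a trough below quantification.* SAP 9.5.2 does say that "BQL values that occur after the first quantifiable point will be considered missing". But at half-lives of 10 to 28 days the trough is far from zero. Falling below 1% of peak by day 15 needs a half-life of about 2 days or less. In such a subject, assuming time-constant elimination, the Week 12 window would remove AUC0-12wk, and the λz rule could remove AUCinf.
- *That an error of this size nearly uses up the distance to 1.25.* That bound applies to a ratio of arm geometric means, not to one subject.
- *That the GMR will be biased.* This needs missing troughs to be unbalanced between arms. The trial is randomized and double-blind, and the documents give no reason to expect imbalance.

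**Conclusion.** The point holds as a defect in a written derivation rule. With a missing day-15 predose sample, SAP 5.2 yields an AUC0-12wk and AUCinf that are too high, and no specific criterion corrects or excludes them, although the same event excludes infusion-2 Cmax. The direction follows from the rule and the sampling schedule alone. The size, roughly 7% to 40% per affected subject, rests on assumed half-lives, profile shapes and infusion times, because the documents give no PK values.

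The likely effect on the trial's conclusion is small. It becomes visible in the GMR only if missing troughs are both frequent and unbalanced, and the documents give no rate. The reason to act is that AUCinf is co-primary and the repair is cheap, not that the PK conclusion is in danger.

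**What to change.** Before unblinding, add to SAP 5.2 that AUC0-12wk and AUCinf are not integrated directly from the 48-hour sample to the day-15 end-of-infusion sample. When the day-15 predose sample is missing, apply one of two rules, chosen in advance:

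1. Extend the existing Day 15 window exclusion to AUC0-12wk and AUCinf. This is the simpler option and needs no modelled value. It costs a few excluded values; power stays at about 95% even with 5 subjects lost per arm.
2. Insert a flagged trough at the start of infusion 2, equal to the last infusion-1 concentration × exp(−λz × elapsed time), and repeat the primary analysis without flagged subjects. This costs one derived record per affected subject and leaves a few AUCs resting on one interpolated point. Where λz is not reliable, the trough cannot be inserted and option 1 should apply.

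Changing to a linear-up/log-down rule would not help, because the false segment is a rising one. No new data are needed.
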